## Description:

- The purpose of this Statistical Analysis Plan (SAP) is to describe the planned analyses and presentation of results in the clinical study report corresponding to the study protocol MAGIC-MT .
- The purpose of this SAP is to describe the efficacy analysis and safety analysis required by the study protocol for middle meningeal artery (MMA) embolization using liquid embolic material for the treatment of non-acute subdural hematoma.
- This SAP will be provided to study team members to communicate the full delivery of the statistical analysis.

## Version History

This SAP is based on the MAGIC-MT study protocol version 3.0 version dated 2022-09-21 .

SAP Version	Effective Date	Author	Revision Description
1.0	2023-12-02	[name]	Original Version

## 1. Summary of Protocol

### 1.1. Statistical Analysis Plan and Protocol Discrepancies

All changes to the content of the analyses originally specified in Protocol 3.0 (2022-09-21) are summarized in Table 1.

**Table 1 Changes to the analysis plan defined in the protocol**

Protocol	Statistical Analysis Plan	
Statistical description in the protocol	Statistical description in statistical analysis plan	Reason for change

 
Section 7.3.1 For the primary endpoint, CMH chi-square analysis will be used to calculate the difference in the event rate between the two groups and its 95% confidence interval, and Kaplan-Meier method will be further used to estimate the event rate of the primary endpoint and its 95% confidence interval.
 
	
 
Section 8.2.2 Primary analysis: 90-day recurrence or progression rates will be summarized for each group using a two-sided 95% CI (Clopper-Pearson method). P-values for differences in recurrence or progression rates between the 2 groups will be compared between groups using the CMH chi-square test. The stratification factor is whether or not trepanation and drainage is performed. In addition, a two-sided 95% CI for the difference in recurrence or progression rates between the two groups will be calculated using the Miettinen-Nurminen method.
 
Sensitivity analysis: Generalized linear mixed-effects model will be used to calculate ORs and their 95% CIs for the comparison of recurrence or progression rates between the two groups for sensitivity analysis with group as a covariate, site as a random
 
	
 
According to internal discussion as well as reference to the design of similar studies, time-to-event analyses were not included for the primary endpoint, and logistic regression analysis methods were added.
 

Protocol	Statistical Analysis Plan	
Statistical description in the protocol	Statistical description in statistical analysis plan	Reason for change
	
effect. Multivariable analysis will also be provided to include group, sex, age, maximum thickness of hematoma on the enrolled side, baseline mRS score.
	

 
Section 7.3.2 The analyses of secondary endpoints will be the same as those for the primary endpoint, and comparisons between groups will be made using the Chi-square test (qualitative measure) or t-test (quantitative measure). For event endpoints, the Kaplan Meier method will be used.
 
	
 
For two continuous secondary endpoints, Change of maximum hematoma thickness and hematoma volume between baseline and 90 days, a linear mixed effects model approach will be used to estimate the mean estimate (95% CI) of change from baseline for both treatment groups and mean estimate (95% CI) of difference between groups and p-value of difference between groups; Treatment group variables, sex, age, surgical treatment strata (trepanation/drainage vs. no trepanation/drainage), any usage of antiplatelet or anticoagulant therapy within one month before randomization(yes vs no), hematoma volume of baseline CT will be included in the model. The random effects will be site. For other continuous secondary endpoints, group comparisons will be performed using t-tests or Mann-Whitney U tests and 95% confidence intervals for
 
	
 
According to internal discussion as well as reference to the design of similar studies, secondary endpoints do not include time-to-event analyses and linear mixed effects model analysis methods are added.
 

Protocol	Statistical Analysis Plan	
Statistical description in the protocol	Statistical description in statistical analysis plan	Reason for change
	the difference in means between groups will be calculated using normal approximation.	

 
None
 
	
 
Section 8.2.1 The results of central imaging assessment analysis of CT/MRI examinations required for the determination of the subject's primary endpoint in this study will be presented in tables. Central image evaluation will be performed by the Independent Central Image Review Committee. Neurological symptoms and follow-up mRS scores were derived from OAC review data.
 
Section 9.3.2.1 CEC assessments for adverse events of special interest.
 
	
 
Added central imaging assessments (CT/MRI examinations), CEC assessments (adverse events of special interest), and clarified data sources.
 

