7.1.1 Test level

Two-sided tests are performed for all hypothesis tests ($\alpha = 0.05$). The confidence level of all confidence intervals is 95%.

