7.1.3 Estimation of sample size

This study hypothesizes that MMA embolization may reduce the recurrence (operation group) or progression (conservative treatment group) of SDH. The estimated recurrence or progression rate of hematoma in the MMA embolization group is 5%, while that of control group is 12%. When estimating bilateral 5% for the statistical significance level, 90% for power, and 8% for an acceptable rate of loss to follow-up, the total sample size is estimated to be 722 cases.

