7.3.2 Secondary efficacy analyses

Summarize the following indicators:

- Recurrence or progression rate of SDH at 360 days post-procedure
- Success rate of target blood vessel embolization (MMA trunk and branch vessels) on DSA imaging
- Change in hematoma thickness on CT/MRI at 90 days post-procedure
- Change in hematoma volume at 90 days post-procedure
- Change in midline shift on CT/MRI at 90 days post-procedure
- Change in mRS score at 90 days and 360 days post-procedure
- Proportion of patients with mRS ≤ 2 at 90 days and 360 days post-procedure
- Proportion of patients with mRS ≤ 3 at 90 days and 360 days post-procedure
- Quality of life evaluated with EQ-5D Scale at 90 days and 360 days post-procedure
- Total hospital length of stay, number of re-hospitalizations, destination for rehabilitation after discharge (home vs. rehabilitation hospital) and total hospitalization expenses

Same as primary endpoint analysis, Chi-square test (qualitative indicator) or t-test (quantitative indicators) is used for inter-group comparison in secondary endpoint analysis.

For time event endpoints, such as incidence of recurrence or progression of SDH at 360 days post-procedure, the KM method will be used.

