## 1.2. Study Objectives and Endpoints

[figure not shown]
Study objectives	Study Endpoints
Primary objective	Primary Study Endpoints

 
To validate that in patients with symptomatic non-acute subdural hematoma (SDH), MMA embolization with liquid embolic materials can reduce a) the incidence of symptomatic hematoma
 
	
 
Incidence of symptomatic recurrence (in patients who undergo trepanation/drainage) or symptomatic progression of hematoma (in patients who do not undergo trepanation/drainage) within 90 days after randomization
 
Symptomatic hematoma recurrence is defined as maximum hematoma thickness >10 mm in patients in
 

Study objectives	Study Endpoints
recurrence for patients receiving trepanation and drainage and b) the incidence of symptomatic hematoma progression for patients undergoing conservative treatment.	
the trepanation group, combined with neurological symptoms, or that the patient needs to undergo re-operation
 
 
Symptomatic hematoma progression is defined as an increase of >3mm maximum thickness of SDH of patients in the non-trepanation group compared with baseline, or the need for surgery based on the assessment of the treating medical team
 

Secondary objectives	Secondary Study End Point

 
To validate the efficacy of MMA embolization with liquid embolic materials
 
	
 
Incidence of SDH symptomatic recurrence (in patients who undergo trepanation/drainage) and symptomatic progression (in patients who do not undergo trepanation/drainage) 360 days after randomization
 
Success rate of target vessel embolization in DSA imaging
 

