## 8.2. Specifications of Primary Efficacy Endpoints Analyses

### 8.2.1. Definitions and Derivations

- **Symptomatic** SDH recurrence (in the trepanation/drainage group) refers to a situation in which the maximum thickness of hematoma of patients exceeds 10 mm, combined with neurological symptoms, or the need for repeat surgery.
- Symptomatic SDH progression (in the non-trepanation/drainage group) refers to a situation in which the maximum thickness of increases by more than 3 mm compared with baseline, combined with neurological symptoms, or the need for surgery.
- The results of central imaging evaluation and analysis of CT/MRI examinations required for the determination of the subject 's primary endpoint in this study will be presented in tables and listings, respectively. Central image evaluation will be performed by the independent Core Lab. Evaluation of neurological symptoms will be derived from the Outcome Assessment Committee (OAC) review data.
- It should be noted that if there is a record of reoperation in participants who have undergone trepanation/drainage, and there is a record of surgical treatment in subjects who have received medical therapy without trepanation/drainage, the occurrence of the primary endpoint can be directly determined, and hematoma thickness or neurological symptoms are no longer required.
- In case of non-negligible amounts of missing data (>5%), we will use the MCMC method based on the Missing at random (MAR) assumption to impute missing data. The regression model will include group, sex, age, BMI, baseline mRS score and baseline maximum

hematoma thickness. The number of imputations is 10, seed=1234, nbiter=200. SAS code examples for multiple imputation will be provided in Appendix 3.

- Hematoma recurrence (trepanation/drainage group) or symptomatic hematoma progression (non-surgical group) at day 90 will be analyzed as follows. If there is any discrepancy between EDC and central imaging assessment scan date in the determination of visit window, the date determined by central imaging assessment shall prevail.

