### 9.1.2.2. Statistical Analysis Methods

- 360 days recurrence or progression of SDH after randomization will be analyzed in the same way as the primary endpoint (Section8.2.2)
- Ordinal logistic regression will be used for intergroup comparison of mRS scale scores at 90 and 360 days after randomization, with treatment group, sex, age, surgical treatment strata (trepanation/drainage vs. no trepanation/drainage), any usage of antiplatelet or anticoagulant therapy within one month before randomization(yes vs no), hematoma volume of baseline CT as covariates.
- Other categorical secondary endpoints will be analyzed in the same way as the primary endpoint **(Error! Reference source not found.Error! Reference source not found.Section)**

- The linear mixed effects model approach will be used to estimate the mean estimate (95% CI) and the mean estimate (95% CI) of the differences between groups as well as the P values of the differences between groups for the change in maximum hematoma thickness at 90 days after randomization compared to baseline and the change in hematoma volume at 90 days after randomization compared to baseline; Treatment group variables, sex, age, surgical treatment strata (trepanation/drainage vs. no trepanation/drainage), any usage of antiplatelet or anticoagulant therapy within one month before randomization(yes vs no), hematoma volume of baseline CT , visit variables, and visit by treatment group variable interactions will be included in the model and site as the random effect.
- For other continuous secondary endpoints, T tests will be used to compare groups, and 95% confidence intervals for the difference in means between groups will be calculated using normal approximation.

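### The SAP replaces the protocol's Kaplan-Meier analysis of 360-day recurrence/progression with a binary analysis whose imputation model leaves out the known day-90 result

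*SAP*

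**What the plan says.** Protocol 7.3.2 gives the method for this endpoint: "For time event endpoints, such as incidence of recurrence or progression of SDH at 360 days post-procedure, the KM method will be used". Protocol 7.1.4 adds that missing values are not imputed.

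SAP Table 1 declares a change. In its words, "secondary endpoints do not include time-to-event analyses and linear mixed effects model analysis methods are added"; the reason given is internal discussion and the design of similar studies. SAP 9.1.2.2 supplies the replacement: "360 days recurrence or progression of SDH after randomization will be analyzed in the same way as the primary endpoint". That means the stratified CMH test with Clopper-Pearson and Miettinen-Nurminen intervals. SAP 9.1.2.1 takes all remaining definitions and derivations from 8.2.1.

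SAP 8.2.1 says that with more than 5% missing, data are imputed by MCMC under missing at random. On the covariates it says: "The regression model will include group, sex, age, BMI, baseline mRS score and baseline maximum" hematoma thickness. The footnote to Table 5 says that with less than 5% missing there is no imputation and a missing result counts as no event. Table 5 is written for the 90-day visit.

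SAP 1.2 lists the 360-day endpoint as an incidence, ending with "symptomatic progression (in patients who do not undergo trepanation/drainage) 360 days after randomization". Neither document gives a derivation rule specific to day 360.

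**The concern.** Kaplan-Meier uses partial follow-up. A patient seen event-free at day 90 (V4) and then lost contributes that event-free time and is censored afterwards. The SAP removes this method and puts nothing in its place that uses the V4 result. Under the imported rules, such a patient looks like one never seen after randomization: the imputed value depends on arm, sex, age, BMI, baseline mRS and baseline thickness only. The patient is given the full 0-360-day risk although the first 90 days are known to be clear.

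Most of the expected risk falls before day 90, and it is higher in the control arm. The false failures therefore fall mainly in controls and widen the 360-day difference.

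There is a second, smaller gap. SAP 8.2.1 counts any recorded operation as an event by itself. It does not say whether an event established at V4 by scan and symptoms, without surgery, counts at day 360 (V5) if the later scan is clear or absent. Two programmers could resolve this differently and report different 360-day rates from the same data.

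**Working it through.** **The plan's own figure.** Protocol 7.1.3 assumes 5% v 12%, a two-sided 5% level, and "90% for power, and 8% for an acceptable rate of loss to follow-up, the total sample size is estimated to be 722 cases". With pooled variance under the null and no continuity correction:

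n per arm = [1.960 × √(2 × 0.085 × 0.915) + 1.2816 × √(0.12 × 0.88 + 0.05 × 0.95)]² / 0.07² = (0.773 + 0.501)² / 0.0049 ≈ 331.5, so 332.

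Total = 664 / 0.92 = 721.7, so 722, or 361 per arm. The figure reproduces. The documents give no 360-day rate, sample size or power, so the rest is an illustration.

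**Inputs.**
- From the documents: 361 per arm; day-90 rates 12% control and 5% embolization (planning values).
- Assumed: cumulative 360-day rates 14% and 6%; 8-15% of each arm lost between V4 and V5, that is 361 × 0.08 ≈ 29 and 361 × 0.15 ≈ 54; all of these event-free at V4; loss unrelated to later risk; V4 events counted at day 360.

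**Correct risk for a patient event-free at V4.**
- Control: (0.14 − 0.12) / 0.88 = 2.27%.
- Embolization: (0.06 − 0.05) / 0.95 = 1.05%.

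**Imputed against expected events.**

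| | Control, 29 lost | Control, 54 lost | Embolization, 29 lost | Embolization, 54 lost |
|---|---|---|---|---|
| Imputed at whole-period risk (14% or 6%) | 4.06 | 7.56 | 1.74 | 3.24 |
| Expected given event-free at V4 | 0.66 | 1.23 | 0.31 | 0.57 |
| Excess | 3.40 | 6.33 | 1.43 | 2.67 |

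**Effect on the difference.**
- 29 lost per arm: (3.40 − 1.43) / 361 = 0.5 point.
- 54 lost per arm: (6.33 − 2.67) / 361 = 1.0 point.

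The true difference on these inputs is 14 − 6 = 8.0 points, so the analysis would target about 8.5-9.0. This is slightly low. If only V4-event-free patients are lost, the retained patients, from whom the model learns, have a higher rate than 14%; for controls with 29 lost it is (361 × 0.14 − 0.66) / 332 = 15.0%.

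**Kaplan-Meier on the same inputs.** The control estimate is 1 − 0.88 × (1 − 0.0227) = 14%, and the embolization estimate is 1 − 0.95 × (1 − 0.0105) = 6%. Both true rates are recovered because the V4 information is used.

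**The branch below 5% missing.** With up to 361 × 0.05 ≈ 18 lost per arm and scored as no event, 18 × 0.0227 = 0.41 control and 18 × 0.0105 = 0.19 embolization events are missed. The difference shrinks by (0.41 − 0.19) / 361 = 0.06 point. This error is small and in the opposite direction.

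**The case against.** The strongest reply is that Table 5 and the imputation rule are written for the 90-day primary endpoint, so applying them at V5 is the reader's own step. That is fair as far as Table 5's column headings go. But 9.1.2.1 refers to 8.2.1 for all other derivations, the imputation model is stated there, and the SAP offers no other rule. The sample code in SAP Appendix 3 does not help: it later transposes two visit variables, but its imputation variable list holds baseline covariates and the outcome only.

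Second, below 5% missing there is no imputation and hence no inflation. This stands. However, the protocol allows for 8% loss, so the imputation branch is realistic. That 8% is a general sample-size allowance, not an estimate of loss between V4 and V5.

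Third, the change is declared, it affects a secondary endpoint, and scheduled imaging after baseline is at V4 and V5 only, so Kaplan-Meier against a binary analysis is largely a choice of method. This also stands. A binary analysis can be cumulative and can use V4 status; this one is not specified to do so.

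A reader might go further and infer that the endpoint is read from V5 alone, so that known day-90 events are dropped and the 360-day incidence can fall below the 90-day incidence. The documents do not support that. The SAP calls the endpoint an incidence, and the protocol uses the same at-360-days wording in the very sentence that assigns Kaplan-Meier. The protocol collects endpoint events at the 30-, 90- and 360-day follow-ups, and recorded operations count in their own right. What remains is an unstated rule for events without surgery.

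Nor is this the only long-term efficacy endpoint: mRS and EQ-5D are also assessed at 360 days.

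**Conclusion.** The concern holds in a limited form. The SAP removes a method that used day-90 follow-up. The imputation model it imports assigns whole-period risk to patients already known to be event-free at day 90. On assumed 360-day rates of 14% v 6% and 8-15% loss between V4 and V5, the treatment difference is inflated by about 0.5-1.0 point. The size scales with the loss and depends on how much of the risk falls before day 90; neither the loss nor the 360-day rates are in the documents. Below 5% missing, the effect is negligible.

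Separately, the SAP should say how V4 events without surgery count at day 360. This is a gap in specification, not evidence that events are discarded, and no size can be put on it from the documents. The primary 90-day analysis is not affected by either point.

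**What to change.** In SAP 9.1.2:

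- Define the endpoint as any qualifying event from randomization to day 360, and count every V4 event whatever V5 shows.
- For patients event-free at V4 without V5 data, impute only the day 90-360 period, with V4 status in the imputation model. Amend the Appendix 3 variable list to match.
- Restore the protocol's Kaplan-Meier estimate of the 360-day rate as a supportive analysis, and revise Table 1 accordingly.
- State in the same place how deaths after day 104 and out-of-window V5 visits are handled in the 360-day analysis, since Table 5 covers the 90-day endpoint only.

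The cost is SAP wording and extra programming; V4 and V5 data are already collected. The drawback is that scan-detected events are dated to the visit, so the Kaplan-Meier curve will step at V4 and V5.

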## 1.2. Study Objectives and Endpoints

[figure not shown]
Study objectives	Study Endpoints
Primary objective	Primary Study Endpoints

 
To validate that in patients with symptomatic non-acute subdural hematoma (SDH), MMA embolization with liquid embolic materials can reduce a) the incidence of symptomatic hematoma
 
	
 
Incidence of symptomatic recurrence (in patients who undergo trepanation/drainage) or symptomatic progression of hematoma (in patients who do not undergo trepanation/drainage) within 90 days after randomization
 
Symptomatic hematoma recurrence is defined as maximum hematoma thickness >10 mm in patients in
 

Study objectives	Study Endpoints
recurrence for patients receiving trepanation and drainage and b) the incidence of symptomatic hematoma progression for patients undergoing conservative treatment.	
the trepanation group, combined with neurological symptoms, or that the patient needs to undergo re-operation
 
 
Symptomatic hematoma progression is defined as an increase of >3mm maximum thickness of SDH of patients in the non-trepanation group compared with baseline, or the need for surgery based on the assessment of the treating medical team
 

Secondary objectives	Secondary Study End Point

 
To validate the efficacy of MMA embolization with liquid embolic materials
 
	
 
Incidence of SDH symptomatic recurrence (in patients who undergo trepanation/drainage) and symptomatic progression (in patients who do not undergo trepanation/drainage) 360 days after randomization
 
Success rate of target vessel embolization in DSA imaging
 


 
To validate the safety of MMA embolization with liquid embolic materials
 
	
 
Serious Adverse Events (SAEs) within 90 days and 360 days
 
Death within 90 days and 360 days
 
Severe surgery-related complications within 30 days after surgery (including trepanation/drainage and MMA embolization): 
 
Symptomatic intracranial hemorrhage
 
Surgery-related intracranial hemorrhage
 
Surgery-related neurological deficits
 
Surgery-related central nervous system infection
 
Surgery-related arterial dissection, vascular wall injury and vascular rupture and perforation
 
Surgery-related ischemia
 
Access site hematoma
 
Neuropathy at the puncture site
 
Contrast allergy or contrast encephalopathy
 
 
 

 
To validate the reduction of residual hematoma at 90 days after randomization in patients
 
	
 
Changes of hematoma thickness on CT/MRI imaging at 90 days after randomization
 

Study objectives	Study Endpoints
undergoing MMA embolization	
 
Changes of hematoma volume at 90 days after randomization
 
Changes of midline shift in CT/MRI imaging at 90 days after randomization
 

 
To validate the improvement in clinical outcome (mRS score) at 90 days and 360 days after randomization in patients undergoing MMA embolization
 
	
 
Changes of Modified Rankin Scale (mRS) score at 90 days and 360 days after randomization
 
Proportion of patients with mRS score of 0 to 2 at 90 days and 360 days after randomization
 
Proportion of patients with mRS score of 0 to 3 at 90 days and 360 days after randomization
 

 
To validate the improvement in health status (EQ-5D-5L scale) at 90 days and 360 days after randomization in patients undergoing MMA embolization
 
	
 
Quality of life evaluated with EQ-5D-5L Scale at 90 days and 360 days after randomization
 


 
To validate the reduction of readmission rate within 90 days after randomization in patients undergoing MMA embolization
 
	
 
Total days of hospital stay, re-hospitalization times, destination for rehabilitation after discharge (going home vs rehabilitation hospital) and total hospitalization expenses
 

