7.2 Safety Analysis

7.2.1 Adverse events

Adverse event (AE) data is described according to the current version of MedDRA and then statistically analyzed.

SAEs within 90 days and 360 days post-procedure and the incidence of serious surgery-related complications within 30 days after surgery are summarized. The incidence of AEs is recorded as 1 case if multiple AEs occur in one patient or the same AE occurs frequently in one patient.

AEs will be summarized by system organ class (SOC) and preferred term (PT) in a frequency table. The incidence is calculated by systems and symptoms/signs (count of cases: the number of subjects with at least one AE).

Severity of AEs: When the same subject has the same AE several times, the most serious one is used to analyze the severity of the AE.

A list of subjects experiencing AEs will be provided.

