## 2. Statistical Hypothesis

Hypothesis testing will be performed on hematoma recurrence or progression rates.

- Null hypothesis: there is no difference in the incidence of recurrence or progression of hematoma between the MMA embolization group and the control group at 90 days after randomization;

- Alternative hypothesis: there is difference in the incidence of recurrence or progression of hematoma between the MMA embolization group and the control group at 90 days after randomization.

The above hypothesis tests will be two-sided and statistical significance will be determined as a p-value of  $<0.05$ , and two-sided 95% confidence intervals will be reported.

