## 6. Considerations for Data Analyses and Data Handling Conventions

Analyses will be performed using SAS ® System Version 9.4 or higher, and all tables, figures, and listings will be generated as RTF files.

For descriptive statistics, the number of observations (n), standard deviation, median, minimum, maximum, Q1 and Q3 will be presented for continuous variables and number and percentage of subjects will be presented for categorical variables, unless otherwise specified.

Table 2 provides an overview of the appendices in the SAP for outlining general rules for data analyses and data handling conventions.

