**Table 6 Planned Overview of Secondary Efficacy Endpoint Analyses**

	Data Presentation Generated		
	Table	Figure	Listing
Incidence of recurrence or progression of SDH at 360 days after randomization: Same as Table 4 Overview of planned primary statistical analyses			
Categorical secondary endpoints: Success rate of target blood vessel embolization in DSA imaging Change in mRS score at 90 days and 360 days after randomization compared to baseline Proportion of patients with mRS score of 0 to 2 at 90 days and 360 days after randomization Proportion of patients with mRS score of 0 to 3 at 90 days and 360 days after randomization Destination for rehabilitation after discharge (going home vs rehabilitation hospital)			
Statistical description of categorical data: Number (n) and percentage of subjects in each category			
Dichotomous data analysis: - Proportion and its 95% CI - Difference in sample rate between MMA embolization and control groups, p-value and 95% CI - OR for MMA embolization and control groups with 95% CI	Y		Y
Continuous Secondary Endpoints: Changes of hematoma thickness in CT or MRI imaging at 90 days after randomization compared to baseline Changes of hematoma volume at 90 days after randomization Changes of midline shift in CT or MRI imaging at 90 days after randomization Changes of mRS score at 90 days and 360 days after randomization Quality of life evaluated with EQ-5D-5L Scale at 90 days and 360 days after randomization Total hospital stay (number of days) Re-hospitalization times Total hospitalization expenses			
Statistical description of continuous data: - Number of non-missing cases (n) - Mean (standard deviation)	Y		Y

	Data Presentation Generated		
	Table	Figure	Listing

 
- Median
 
- Min, Max
 
- Q1,Q3
 
 
Continuous data analysis:
 
 
- Estimate of mean and 95% CI for MMA embolization and control groups
 
- Difference in means and 95% CI between MMA embolization and control groups
 
- P value for difference in means between MMA embolization and control groups
 
			

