## **9.2.2 Specifications Of Safety Analyses**

### **9.2.2.1 Adverse Events**

- An untoward medical occurrence during a clinical investigation, whether or not related to the investigational medical device, is an adverse event (AE).
- AEs will be coded using MedDRA version 24.0 or higher. System Organ Class (SOC) and Preferred Term (PT) will be reported.
- The investigator will grade the severity of the AE (mild, moderate, severe). AEs with missing severity will not be imputed.
- Adverse events will be summarized using frequency tables in descending order of incidence by SOC and PT unless otherwise specified. If a subject has the same AE reported more than once, the highest severity of this AE for that subject will be reported.
- For adverse events of special interest, the CEC assessment and investigator assessment will be performed, and the results of the two assessments will be presented separately.

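### The safety objective is to 'validate' safety, but the SAP plans only counts and percentages, with no margin, between-arm difference or confidence interval, so the output cannot show how much excess harm remains possible

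*SAP*

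**What the plan says.** The SAP states the objective in section 1.2: "To validate the safety of MMA embolization with liquid embolic materials". It attaches SAEs and death, each at 90 and 360 days, and severe surgery-related complications within 30 days. Protocol section 2 also uses 'validate' for safety.

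The analysis is in SAP 9.2. Table 7 lists tables and listings, with every block footnoted as categorical data. The general rule in SAP section 6 for such data is that "number and percentage of subjects will be presented for categorical variables, unless otherwise specified". For adverse events, SAP 9.2.2.1 says: "Adverse events will be summarized using frequency tables in descending order of incidence by SOC and PT unless otherwise specified". The SAP's only formal hypothesis is for efficacy (section 2): "Hypothesis testing will be performed on hematoma recurrence or progression rates".

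For categorical secondary efficacy endpoints, Table 6 plans more: "Difference in sample rate between MMA embolization and control groups, p-value and 95% CI". SAP 9.1.2.2 applies the primary-endpoint methods to other categorical secondary endpoints, but that rule sits within the secondary efficacy section.

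Protocol 7.2.1 says that AE data "is described according to the current version of MedDRA and then statistically analyzed". It names no method, and then describes summaries and frequency tables.

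**The concern.** An objective to validate something needs either a criterion or an estimate with its uncertainty. The safety objective has neither. Neither document states an acceptable excess, an expected safety event rate, or a between-arm comparison for SAEs, death or severe complications.

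This matters because embolization is an endovascular procedure added to the care that controls also receive. The natural safety question is how much extra harm, if any, it brings. Two columns of percentages answer that only by eye. Near-equal columns can look reassuring although the data still allow a material excess, and no planned output would put a figure on it.

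**Working it through.** **Inputs.** From SAP section 3: 12% v 5%, two-sided alpha 0.05, 90% power, 8% loss, 722 in total. From SAP 1.3: 1:1 allocation. The documents give no safety event rates, so every safety rate and count below is an assumption.

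**1. The plan's own figure.** Pooled-variance formula for two proportions, with mean rate 0.085:

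n = [1.960·√(2·0.085·0.915) + 1.282·√(0.12·0.88 + 0.05·0.95)]² / 0.07² = 331.5, so 332 per arm.

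332 / 0.92 = 360.9, so 361 per arm and 722 in total. The figure reproduces exactly. It is sized for efficacy only.

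**2. What equal observed rates leave open.** Half-width of the 95% CI for a risk difference = 1.96·√(2p(1−p)/361):

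- p = 2%: 1.96·√(0.0392/361) = 2.0 points
- p = 5%: 1.96·√(0.0950/361) = 3.2 points
- p = 10%: 1.96·√(0.1800/361) = 4.4 points

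For scale, the efficacy benefit assumed in the plan is 12 − 5 = 7 points.

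**3. What the proposed intervals would show.** Score (Miettinen-Nurminen) 95% intervals for illustrative counts out of 361 per arm:

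| Embolization v control | 95% interval for difference (points) |
|---|---|
| 4 v 4 | −1.8 to +1.8 |
| 8 v 4 | −0.9 to +3.3 |
| 18 v 18 | −3.3 to +3.3 |
| 36 v 36 | −4.4 to +4.4 |
| 54 v 36 | +0.2 to +9.9 |

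For a complication confined to the embolization arm, zero events in 361 gives an exact two-sided 95% upper limit of 1 − 0.025^(1/361) = 1.0%.

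**4. How often a real excess would reach significance if it were tested.** The SAP plans no such test; this only gauges what 361 per arm can reveal. All pairs of binomial counts were enumerated, and the probability of a two-sided 5% Pearson chi-square result in the harmful direction was summed:

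| Control v embolization (assumed) | Power |
|---|---|
| 1% v 2% | 17% |
| 2% v 4% | 35% |
| 3% v 6% | 50% |
| 5% v 7.5% | 29% |
| 5% v 10% | 73% |
| 10% v 15% | 53% |
| 10% v 20% | 97% |
| 20% v 30% | 88% |

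With 332 per arm, after 8% loss, these fall by at most about 4 points. A doubling crosses the even-chance line at a control rate of about 3%.

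**The case against.** Descriptive safety reporting is usual, and several features of the plan limit the damage.

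- An independent DSMB reviews safety data, and the CEC assesses at least all protocol-specified safety endpoints (Protocol 11.4 and 11.5).
- All-cause death counts as a primary event (Protocol 7.3.1; to day 104 in SAP Table 5). SAP Table 4 shows it by arm, and the composite gets a Miettinen-Nurminen interval.
- The mRS comparisons would partly reveal disabling harm.
- 'Validate' is used across the SAP's objectives, and the protocol synopsis has 'assess' for several of them, which suggests loose drafting. The safety item, however, reads 'validate' in the synopsis too.
- A reader can compute an interval from the tabulated counts.

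Most of this stands as mitigation. None of it supplies a separate comparative safety estimate. Monitoring and adjudication are not a final estimate. In the composite, fewer recurrences can offset more deaths, and SAEs and procedural complications as such are not part of it. That the interval is easy to compute is a reason to prespecify it.

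Two stronger readings are tempting, and the documents support neither:

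- A reader might infer that 722 patients would usually miss a harm. That depends on rates the documents do not give. It holds for doublings from a control rate below about 3% and for some moderate excesses such as 5% v 7.5%, but not for 5% v 10% or 10% v 20%. SAEs are defined broadly (Protocol 10.2, including hospitalization), so their rates need not be that low.
- A reader might infer that safety will be declared from a non-significant test, by joining "Two-sided tests are performed for all hypothesis tests" (Protocol 7.1.1) to the statement that AE data are statistically analyzed (Protocol 7.2.1). The first sets the level for whatever tests are done; the second names no test. SAP 9.2 plans none. A claim resting on no visible excess is likewise an inference, not a written rule.

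A doubling model also fits access-site and contrast events poorly. Both flow charts mark DSA as done only in the embolization arm, so these events should be near zero in controls, and a one-arm rate with an interval is more useful. Protocol 6.5 lists DSA among examinations before randomization without that restriction; the passages must be reconciled.

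**Conclusion.** The point holds as a mismatch between objective and output. The SAP sets out to validate safety but plans neither a criterion nor a between-arm estimate with uncertainty, although it plans exactly that for categorical efficacy endpoints. At 361 per arm, equal observed rates of 2% to 10% would leave an excess of roughly 2 to 4.4 points unexcluded, and no planned table would say so. These figures rest on assumed rates and full follow-up; the intervals would be slightly wider with losses.

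The omission biases no estimate and leaves the primary efficacy inference untouched. It is worth correcting because it is cheap and lets the trial answer its own safety question.

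**What to change.** In SAP 9.2 and Table 7:

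1. Add the between-arm risk difference with a two-sided 95% Miettinen-Nurminen CI for SAEs (90 and 360 days), death (90 and 360 days) and 30-day severe surgery-related complications. The method is already coded in SAP 8.2.3.1. No p-values are needed.
2. For the existing Table 7 row on complications of embolization, add the embolization-arm rate with an exact (Clopper-Pearson) 95% CI, also coded there.
3. In SAP 1.2, change 'validate' to 'estimate' for safety. State that the conclusion is the upper confidence limit, meaning the largest excess not excluded, and that absence of a visible or significant difference will not be reported as evidence of safety.
4. Settle what the new rows need: one denominator (the Safety Set in SAP section 5 lists all randomized, as treated and ITT together) and one clock (SAP 1.2 counts the 30 days from surgery, Table 7 from randomization).

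If the sponsor prefers to keep 'validate', a justified margin must be fixed in advance. As illustration only, with equal true rates and one-sided 0.025, power = Φ(margin/√(2p(1−p)/361) − 1.96). A 5-point excess would be excluded with 87% power at a 5% rate and 61% at 10%. A 3-point excess would be excluded with 82% power at 2% and 46% at 5%.

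The cost is SAP wording, a few table rows from existing code, and a more modest safety claim. No new data or patients are needed.
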